## Hypothesis

VCO Therapeutic Contact Lens can be significantly used to improve tear volume and tear stability in dry eye subjects.

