## STATISTICAL ANALYSIS

After the data has been collected, IBM SPSS Statistics Version 25 (Armonk, NY, USA) will be use to analyze the data. The assessment of the efficacy will be based on the all subjects who completed the study. Shapiro-Wilk test will be used to test the normality of the data as the sample size is less than 100. All results are expressed as Mean  $\pm$  SD. **Parametric test of Repeated Measured Anova** will be used to analyze the statistical difference of before, immediately and after treatment if the data is normally distributed. A probability value ( $p$ -value)  $<0.05$  will indicate that the data is statistically significance.

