#### **Phase 1**

First measurement of TBUT (Mcmonnies, 2018) on both eyes will be taken before lens insertion. Then, subjects will be fitted with therapeutic VCO contact lens on one of their eyes and a placebo hydrogel contact lens on the other eye which acts as a control. The contact lenses will be fitted in randomized manner by a mask operator. Subjects will wear the contact lenses for 15 minutes. After the 15th minute, both contact lenses will be removed and second measurements of TBUT will be done. All tear breakup time (TBUT) measurements will be taken three times and the average value will be used as the data. These will be the immediate measurement after therapeutic VCO contact lens wear. Subjects will be given 15 minutes time interval before a re-measurement of TBUT test again. Once all the measurements are taken, subjects will be discharged from the study before being called again in Phase 2. From the data collected, an analysis will assist to understand the mechanism of tear integrity when VCO therapeutic contact lens is used on dry eyes.

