#### **Phase 2**

First measurement using Schimer's Test (Miyake et al, 2016) on both eyes will be taken before lens insertion. Then, subjects will be fitted with therapeutic VCO contact lens on one of their eyes and a placebo hydrogel contact lens on the other eye which acts as a control. The contact lenses will be fitted in randomized manner by a mask operator. Subjects will wear the contact lenses for 15 minutes. After the 15th minute, both contact lenses will be removed and second measurements of Schimer's Test will be done. All measurements will be taken three times and the average value will be used as the data. These will be the immediate measurement after therapeutic VCO contact lens wear. Subjects will be given 15 minutes time interval before a re-measurement of Schimer's Test again. Once all the measurements are taken, subjects will be discharged from the study before being called again in Phase 3. From the data collected, an analysis will assist to understand the mechanism of tear volume changes when VCO therapeutic contact lens is used on dry eyes.

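### The only stated efficacy test compares time points and names no VCO-eye versus placebo-eye contrast, so a change shared by both eyes could be read as a VCO effect

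*Combined protocol and SAP*

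**What the plan says.** The STATISTICAL ANALYSIS section of the combined protocol and SAP contains one inferential efficacy analysis. It is a "Parametric test of Repeated Measured Anova" which "will be used to analyze the statistical difference of before, immediately and after treatment if the data is normally distributed", judged at p < 0.05. The levels listed are three time points. The section names no lens or eye factor, no lens-by-time interaction and no VCO-minus-placebo contrast. It does not say whether the data are the VCO eye alone, the two eyes averaged, or both eyes with lens as a second factor.

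The design does include a concurrent control. In Phase 1 the VCO lens goes in one eye and "a placebo hydrogel contact lens on the other eye which acts as a control", with the lenses allocated at random and the operator masked. Phases 2 to 4 repeat this. The first TBUT reading "on both eyes will be taken before lens insertion". After 15 minutes of wear "both contact lenses will be removed and second measurements of TBUT will be done", and a third reading follows 15 minutes later. Phase 2 does the same with the Schirmer test: "both contact lenses will be removed and second measurements of Schimer's Test will be done".

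The Hypothesis section states that "VCO Therapeutic Contact Lens can be significantly used to improve tear volume and tear stability in dry eye subjects". Neither it nor the Objective section names a comparator.

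**The concern.** The hypothesis is about the VCO lens. Both eyes also undergo lens insertion, 15 minutes of wear, removal and repeated tear testing, and any of these could move TBUT or Schirmer readings whatever the lens carries. A test over time, whether in the VCO eye or averaged over both eyes, picks up the sum of those influences and any VCO effect, and cannot divide one from the other.

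The randomised fellow eye can make that division, because it shares everything except VCO. The stated analysis does not use it. If both eyes improve together, the planned test can be significant and be reported as VCO efficacy when VCO did nothing. If both eyes worsen, a real VCO benefit could be hidden. Leaving the contrast unstated also leaves the choice of eye, time point and comparison open until the data have been seen.

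**Working it through.** **No figure to reproduce.** The documents give 50 subjects and p < 0.05, but no effect size, SD, correlation or power. The check has two parts: whether any section supplies the missing contrast, and what its absence could cost.

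**1. Search for a between-eye test**

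| Section | What it contributes | Between-eye test? |
|---|---|---|
| Hypothesis, Objective | Improvement or change with the VCO lens | No comparator named |
| STATISTICAL ANALYSIS | ANOVA over three times | None |
| Phases 1 and 2 | Randomised placebo eye; an unspecified analysis to help understand mechanism | None |
| Phases 3 and 4 | Same layout; an unspecified analysis of variability | None |

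**2. Illustration of size**

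From the documents: n = 50, three times, significance level 0.05. Assumed: no VCO effect; an improvement of d SD at removal, equal in both eyes; within-eye correlation r = 0.5 or 0.7; fellow-eye correlation ρ = 0.6. The time means are (0, d, d/2) if the change halves by the third reading, or (0, d, d) if it is sustained.

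The time test has 2 and 2 × 49 = 98 degrees of freedom, with critical F 3.089. Its rejection rate comes from a noncentral F distribution:

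- VCO eye only: λ = 50 × SS / (1 − r), where SS is the sum of squared deviations of the three time means.
- Averaged over both eyes: the same λ divided by (1 + ρ)/2 = 0.8, assuming the eye and time correlations multiply.

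Worked example, d = 0.2, halving, r = 0.5. The means are 0, 0.2, 0.1 and their average is 0.1, so SS = 0.01 + 0.01 + 0 = 0.02. In the VCO eye λ = 50 × 0.02 / 0.5 = 2.0, which gives 22.0%. Averaged over both eyes λ = 2.0 / 0.8 = 2.5, which gives 26.6%.

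Time test significant with no VCO effect (range over r = 0.5 to 0.7):

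| Shared shift | VCO eye, halving | VCO eye, sustained | Both eyes averaged, halving | Both eyes averaged, sustained |
|---|---|---|---|---|
| 0.1 SD | 9–12% | 10–14% | 10–13% | 12–16% |
| 0.2 SD | 22–34% | 28–44% | 27–42% | 34–54% |
| 0.3 SD | 45–67% | 57–80% | 54–78% | 67–89% |

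With ρ from 0.3 to 0.8, the averaged halving figures widen to 24–50% at 0.2 SD and 49–86% at 0.3 SD.

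**3. The between-eye contrast in the same settings**

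In simulation (20,000 trials per setting, d = 0.1 to 0.3, both shapes), the VCO-minus-placebo difference in change at removal is significant in 4.8–5.3% of trials by paired t and 4.8–5.2% by Wilcoxon signed-rank. The paired t is significant in favour of VCO in 2.3–2.7%. At 15 minutes after removal the paired t gives 4.7–5.3%. With skewed (lognormal) data both tests stay between 4.7% and 5.1% at removal.

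**4. A second covariance model**

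A separate simulation built from variance components, with a sustained shift, gives 28% and 44% for the VCO eye at 0.2 SD (r = 0.5 and 0.7). It gives 41% and 62% for the time effect over both eyes, and 4.8–5.2% for eye-by-time in every setting. With no shared shift, all the tests are near 5%.

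**The case against.** The strongest reply is that this is an omission and not a wrong analysis. The ANOVA is named without a factor list, so a lens-by-time model with lens as a second within-subject factor would fit the wording, and a fellow eye described as a control suggests that a comparison was intended. That reading is possible. But the section does not state it, and even a two-factor ANOVA yields a time main effect, which is the only effect the section describes. The interaction or contrast would still have to be named as the efficacy test.

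Testing each eye separately and comparing the verdicts is not stated either, and it would not work. In the second simulation, VCO eye significant and placebo eye not occurred in up to about 20% of trials with no VCO effect.

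It is also fair to say that the documents offer no evidence of a shared improvement, that a shared worsening is equally possible, and that the rates depend on the model. All of this stands. The percentages are therefore illustrations, and the 0.1 SD row shows how mild the problem could be. The logical gap does not depend on them.

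Finally, a single time point is partly a preference. The objectives list the two post-wear times separately, and the eye-by-time test over all three times also held about 5%. What is needed is that the between-eye contrast and its timing are fixed in advance.

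**Conclusion.** The concern holds. Followed as written, the plan yields a time effect that cannot support or refute the hypothesis about VCO, while the randomised placebo eye that could do so is left out of the analysis. Because this is the only efficacy test, it must be fixed before the data are analysed.

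The size for this trial is unknown. Under the stated assumptions, a shared improvement of 0.1 to 0.3 SD with no VCO effect makes the VCO-eye time test significant in roughly 9% to 80% of trials, depending on shift, shape and within-eye correlation. The between-eye contrast remains at about 5%. These are not estimates of the trial's actual error rate. The conclusion that the test does not isolate VCO needs none of them.

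**What to change.** In STATISTICAL ANALYSIS, state that efficacy is judged, for TBUT in Phase 1 and for Schirmer in Phase 2, by the within-subject VCO-minus-placebo difference in change from the pre-insertion reading, at a time point named in advance, reported with a 95% CI. Use a paired t-test, or the same single contrast from a lens-by-time repeated-measures model. If the differences are not normally distributed, use a Wilcoxon signed-rank test on the between-eye difference in change. Present changes over time within each eye as descriptive.

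In Phases 1 and 2, state that both eyes are measured at all three times. At present this is explicit only for the first reading and is implied for the later two by the removal of both lenses.

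The cost is wording only, with no extra subjects or visits, provided both eyes are measured each time. With 50 pairs and two-sided 0.05, the contrast has 80% power for a standardised paired difference of about (1.960 + 0.842)/√50 = 0.40 by the normal approximation.

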## Exec Summary

Dry eyes is an extremely common symptom that affects as many as 337 million people globally. Almost everyone has probably had or will have dry eyes at some point in their life. Common treatment to dry eyes is by using lens lubricant or eye drops which gives short relief and comfort. Sufferers would have to endure the discomfort of having to instill drops frequently for which will indirectly affect their work and quality of life. This study will determine the role of VCO therapeutic contact Lens in changing the tear volume and improving tear stability on dry eyes patients by giving a long relief and effective remedy.

The study will be conducted at UKM Optometry Clinic using randomized, double-masked on 50 dry eye subjects in 4 different phases. Measurement of tears before and after (15 minutes) the therapeutic VCO contact lens are worn by the subjects will be recorded. Similar parameter will be measured 15 minutes post wear (Phase 1 & 2). The intra-variability and inter-variability of the parameters will also be measured accordingly after 2 months (Phase 3 & 4).

The outcome of this study is expected to enhance the volume and stability of tears in dry eye subjects. Sufferers of these symptoms will find prolonged relief through this new knowledge of management, thus will improve the quality of life of people who has dry eyes problems.

VCO therapeutic contact lens may provide the solution of prolonged relief for dry eye symptoms. This will provide a new knowledge amongst eyecare practitioners in managing patients with dry eyes due to ocular disease or environmental factors and using a local product will indirectly boost the economic growth of Malaysia.

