## Objective

The main aim of research is to investigate the changes of tear volume and tear stability from VCO Therapeutic Contact Lens wear.

The following specific objectives are: -

- (i) To determine the tear break up time (TBUT) and tear volume (Schirmer's Test) at 0 and 15 minutes after therapeutic VCO contact lens wear.
- (ii) To determine the tear break up time (TBUT) and tear volume (Schirmer's Test) at 15 minutes after lens removal.
- (iii) To measure the inter-variability and intra-variability of the parameters measured for TBUT, after therapeutic VCO contact lens wear

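### No contrast is named for the value 15 minutes after lens removal (objective ii), so the overall ANOVA cannot show whether a VCO effect is present then

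*Combined protocol and SAP*

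**What the plan says.** The Objective section lists three specific objectives without ranking them. The second is to determine TBUT and Schirmer values "at 15 minutes after lens removal". Phase 1 collects this value for TBUT ("Subjects will be given 15 minutes time interval before a re-measurement of TBUT test again") and Phase 2 for Schirmer ("Subjects will be given 15 minutes time interval before a re-measurement of Schimer's Test again"). In both phases the fellow eye wears a comparison lens: "a placebo hydrogel contact lens on the other eye which acts as a control".

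The Statistical Analysis section is one paragraph. It plans a repeated-measures ANOVA, if the data are normal, that "will be used to analyze the statistical difference of before, immediately and after treatment", with significance at p < 0.05. For description it says "All results are expressed as Mean" ± SD. The documents name no pairwise or post hoc test, no contrast, no multiplicity rule, no confidence interval and no eye-by-time term.

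The Hypothesis section states that the lens "can be significantly used to improve tear volume and tear stability in dry eye subjects", and the Exec Summary expects that "Sufferers of these symptoms will find prolonged relief through this new knowledge of management".

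**The concern.** The 15-minute measurement is the only one within a session that follows the immediate post-removal reading. It is therefore the only evidence on whether anything remains once the lens has been out for a while. The planned F test asks whether the three time means are all equal. Rejecting that does not say which time differs from which. A rise that has vanished by 15 minutes, one that is fully kept and one that appears only at 15 minutes can all produce a significant F.

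The control eye matters for the same objective. A change from before insertion in the VCO eye alone could come from wearing any lens for 15 minutes or from repeated testing. Attributing it to VCO needs the between-eye comparison for which the design collects data, and the analysis paragraph does not say how that eye enters.

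At stake is whether the trial can support any statement about an effect after removal, with a test and a measure of precision behind it.

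**Working it through.** The plan has no figure to reproduce. It gives 50 subjects and p < 0.05, but no power, effect size, SD or correlation.

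**Inputs.** From the documents: n = 50, three times, alpha 0.05. Assumed: a standardised rise d of 0.3 to 0.5, and a correlation rho between times of 0.3 to 0.7. Values are in SD of whatever quantity is analysed.

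**1. Overall F under sphericity** (equal variances and correlations). Degrees of freedom are 2 and (50 − 1) × 2 = 98. The noncentrality is 50 × SS / (1 − rho), where SS is the sum of squared deviations of the three means from their average.

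- Gone by 15 minutes, means (0, d, 0): SS = 2d²/3.
- Fully lasts, means (0, d, d): SS = 2d²/3.
- Half lasts, means (0, d, d/2): SS = d²/2.

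The first two are algebraically identical, so under sphericity the F has the same power for both at any d and rho. With d = 0.5 and rho = 0.5:

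- Gone or fully lasts: SS = 0.1667, noncentrality = 50 × 0.1667 / 0.5 = 16.67, power 0.958 for each.
- Half lasts: SS = 0.125, noncentrality = 12.5, power 0.886.

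At d = 0.3, rho = 0.3 the power is 0.430 for both gone and lasts. At d = 0.5, rho = 0.7 it is 0.998 for both.

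**2. Without sphericity** (simulation, 20,000 runs, d = 0.4). Correlations are listed as before–immediate / before–15 min / immediate–15 min.

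- 0.5/0.3/0.7: gone 0.894, lasts 0.775.
- 0.3/0.7/0.3: gone 0.711, lasts 0.814.

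The two powers now differ, by 12 points one way and 10 the other. A significant F is still common when the effect has gone, and in the first case it is more common than when the effect lasts.

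**3. A named 15-minute comparison** (simulation, 40,000 runs). These are paired t-tests of change from before insertion at each of the two later times, with 49 df and Holm over the two. Power is in SD of the between-eye difference. Results for the 15-minute test at d = 0.5, rho = 0.5:

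- Gone: 0.044.
- Half lasts: 0.403.
- Fully lasts: 0.921.
- Appears only at 15 minutes: 0.885.

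For a fully lasting effect the range runs from 0.353 (d = 0.3, rho = 0.3) to 0.993 (d = 0.5, rho = 0.7).

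**4. If d is in single-eye SD.** Suppose the placebo eye is unchanged and the between-eye correlation is r. The between-eye difference then has SD √(2(1 − r)), so the effective d is 0.5 / √(2(1 − r)). With rho = 0.5:

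- r = 0.2: effective d 0.395, power about 73%.
- r = 0.4: effective d 0.456, power about 86%.
- r = 0.5: effective d 0.500, power about 92%.
- r = 0.6: effective d 0.559, power about 97%.

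**5. False positives.** Holm holds the rate at or below 5% within one outcome (0.047 in simulation under no effect). Over two independent outcomes it is 1 − 0.95² = 0.0975.

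**The case against.** The best reply is that nothing here is a wrong test. The 15-minute value is already a level of the ANOVA, pairwise follow-up is a routine step after a significant F, and objective (ii) asks only to determine a value, which a mean with SD does. The Hypothesis section names no time point, and the relief mentioned in the Exec Summary is an anticipated benefit.

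Part of this stands. A reader might infer that the 15-minute data go unanalysed, but the analysis paragraph includes them. A reader might also infer that the sponsor intends to treat a significant F as proof of a lasting effect, but no section says so. The misreading is possible, not planned.

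The rest does not remove the gap. Routine follow-up is not a commitment: the plan fixes neither the contrast, nor the adjustment, nor the use of the control eye, so all three could be chosen after the data are seen. A mean and SD at each time give no precision for a within-subject change. The trial also hypothesises improvement and expects relief to be prolonged, which calls for inference at the only later time measured.

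A fair objection to the remedy is that setting 92% against the ANOVA's 96% is like for like only if both analyse the between-eye difference. The plan does not say that its ANOVA does, so the power cost is known only conditionally.

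**Conclusion.** The point holds as a missing named comparison, and the plan should be changed before analysis. As written, a significant F cannot show whether a VCO effect is present 15 minutes after removal. Under sphericity its power is the same for a vanished and a fully lasting effect: 96% for each at n = 50, d = 0.5 and rho = 0.5. That equality is algebra and does not depend on d or rho. It does depend on sphericity, and without it the powers differ by about 10 to 12 points in the two cases shown, in opposite directions.

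The percentages rest on assumed effect sizes and correlations. It would go too far to read this as evidence that the effect fades, or that the ANOVA is invalid for the question it asks. The documents support neither reading.

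**What to change.** Add to the Statistical Analysis section:

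> For TBUT (Phase 1) and Schirmer (Phase 2), objective (ii) is tested as the VCO-eye minus placebo-eye difference in change from before insertion to 15 minutes after removal, by paired t-test with 95% CI (Wilcoxon signed-rank if not normal). The same comparison immediately after removal is tested separately, with Holm adjustment across the two time points within each outcome. The change in the between-eye difference from immediately after removal to 15 minutes after is reported with a 95% CI, as an estimate only. A significant 15-minute comparison is reported as an effect present 15 minutes after removal; it is called lasting only if the immediate comparison is also significant in the same direction. A non-significant 15-minute result is not reported as evidence that the effect has gone; the CI is given.

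The 15-minute test does not depend on the immediate test being significant, so an effect that appears late is not lost. The wording keeps such an effect from being called lasting. Phases 3 and 4 stay with the variability objective (iii).

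The cost is one paragraph, with no new visit, measurement or subject. There are four limits to accept:

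- Power for a fully lasting effect may be as low as about 35% within the assumed range.
- If half the effect lasts, power is about 40% at d = 0.5 and rho = 0.5, which is why non-significance must not be read as absence.
- The chance of any false positive over the two outcomes can reach about 10%.
- Nothing can be said beyond 15 minutes after removal.

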## Methodology

The study will be conducted at Optometry clinic UKM KL. Random sampling and double mask method will be used as in this study. A total of 50 subjects who meet the inclusion criteria will be invited to participate in this study once the ethics has been granted. The purpose of the study will be explained to the subjects and consent will be taken if agreeable to participate in the study. Enrollment of subjects and clinical trial will be carried out in staggered period within 5 weeks for each phase.

### Inclusion Criteria:

- a. Healthy male and female
- b. Age: 20 to 40 years old
- c. OSDI scores more than 15

#### Exclusion Criteria:

- a. Subjects with ocular surface diseases such as meibomian gland blockage, meibomianitis and blepharitis
- b. Subjects currently under topical anti-glaucoma and anti-inflammatory eye drops
- c. Subjects with autonomic neuropathy and micro vascular disease e.g diabetic mellitus
- d. Pregnant woman and woman who currently active in breastfeeding.

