## Research Question

## Literature review

Dry eye is an ocular condition which is characterized by reduction in tear volume, tear stability and increase in tear osmolarity as well as water evaporation. Visual disturbances including blurriness, visual discomfort and damage of the ocular surface are the most common dry eye-related sign and symptoms. Previous study had reported that 25 % of patients who visited ophthalmic clinic may report symptoms of dry eye. Thus, making this condition as one of the public health. The current study of dry eye prevalence of in Kuala Lumpur, Malaysia, showed the results of estimation that around 15% of the sample population suffering dry eye (Kaur et.al., 2016). However, the prevalence of dry eye varies between countries and was estimated to be around 7.4% to 33.7% (Buckley, 2018).

To ensure the accuracy of dry eye diagnosis, different tests of tear parameters including tear quantity and quality tests are used to detect the pre-existing condition (Masmali et al. 2016). One of the ways to assess for tear quality is by assessing the stability of the tear film which can be obtained through tear break up time (TBUT) measurement. Tear quantity can be obtained by measuring the tear volume and Schirmer's test is one of the objective measurements that is widely used by the practitioner to measure it (Miyake et. al, 2016). It becomes practically important as stability of the tear film and sufficient composition of each substances such as lipid, mucin, electrolytes, and including aqueous humor, are crucial in order to know the integrity of the tear film layer (Buckley, 2018).

At present, there are few dry eye remedies available in the market. Among all of those remedies, artificial tear and eye lubricants are still the most common initial management and prophylaxis that will be given by medical practitioners to dry eye patient regardless of the type of dry eye. Artificial tear is well known to given temporary relief of dry eye's sign and symptoms. Though, it might not be an effective treatment as they only contain polymers that is able to lubricate ocular surface and lack of numerous important biological factors such as antimicrobial growth and anti-inflammatory factors that present in natural tear and important to maintain ocular surface homeostasis (Mutalib et al. 2015)

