#### Protocol:

Subjects will be required to fill up the consent form and history taking will be carried out on all subjects. Subjects will be tested using the Ocular Surface Disease Questionnaire (OSDI) (Ngo et al., 2017) before recruitment in order to classify subjects if they have dry eye symptoms (inclusion criteria). Visual acuity testing using log MAR Acuity Chart (Johnston, 2016) as well as anterior segment assessment using slit lamp biomicroscopy will be done prior to the study in order to know the baseline Visual acuity and ocular condition of the subjects' eyes.

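### No interval is set between the last lubricant drop or contact-lens wear and the pre-lens reading, so some baselines can carry a residual effect into the over-time comparison

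*Combined protocol and SAP*

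**What the plan says.** **Entry.** Inclusion Criteria asks for healthy adults aged 20 to 40 with "OSDI scores more than 15". Exclusion Criteria has two items on ocular disease and eye drops: "Subjects with ocular surface diseases such as meibomian gland blockage, meibomianitis and blepharitis" and "Subjects currently under topical anti-glaucoma and anti-inflammatory eye drops". Neither list mentions artificial tears, lubricants or habitual contact-lens wear.

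**Screening.** Under Protocol, "history taking will be carried out on all subjects". No rule follows from what the history shows, and time since last use is not listed as an item to record.

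**Baseline.** Phase 1 states: "First measurement of TBUT (Mcmonnies, 2018) on both eyes will be taken before lens insertion". Phase 2 (Schirmer) and Phases 3 and 4 (TBUT) use the same instruction. None of the four refers to the last drop or the last lens worn.

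**Likely use.** The Literature review says that "artificial tear and eye lubricants are still the most common initial management and prophylaxis", and the Exec Summary says "Sufferers would have to endure the discomfort of having to instill drops frequently".

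**Analysis.** Statistical Analysis names one test, a repeated-measures ANOVA over the three time points. It states no contrast between the VCO eye and the placebo eye.

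**The concern.** Objectives (i) and (ii) are read as change from the pre-lens value within a session that includes 15 minutes of wear and a further 15 minutes after removal. If a lubricant has recently raised the baseline and then clears, the reading falls for a reason unrelated to VCO, and a real gain is hidden. If recent lens wear has lowered the baseline, recovery would look like a gain. The documents do not say which happens, or how often.

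Timing of use can also differ between visits two months apart. A TBUT variability computed from baselines or from changes would then include that timing. Because the plan does not call for the timing to be recorded, no later analysis could separate it or adjust for it.

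**Working it through.** The plan gives 50 subjects (Methodology) and a significance level of 0.05 (Statistical Analysis), but no effect size, SD, power or frequency of lubricant use. There is no stated calculation to reproduce. Everything below except n = 50 and 0.05 is assumed, and serves to show which quantities are exposed.

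**1. Bias in the mean change.** Let a share p of subjects have a baseline raised by d seconds, with a fraction k of that effect still present at the post-wear reading. The bias is -p × d × (1 - k). With full clearance (k = 0):
- p = 0.2, d = 1 s: -0.2 s
- p = 0.3, d = 2 s: -0.6 s
- p = 0.4, d = 3 s: -1.2 s

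A lowered baseline reverses the sign.

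**2. Consequence for the test over time.** Use a paired normal approximation, n = 50, two-sided 0.05, change-score SD set to 1. The change detectable with 80% power is (1.960 + 0.842)/√50 = 0.396 SD. Let a fraction f have baselines raised by r SD that clear fully. The bias is -f × r, the SD of change becomes √(1 + f(1 - f)r²), and power = Φ[(0.396 - f × r)√50/SD - 1.960].

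| f | r | bias | SD | power |
|---|---|---|---|---|
| 0.1 | 0.25 | -0.025 | 1.003 | 74% |
| 0.3 | 0.5 | -0.15 | 1.026 | 40% |
| 0.3 | 1.0 | -0.30 | 1.100 | 9% |

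**3. The between-eye contrast.** If the residual is d in both eyes and clears equally, the VCO-minus-placebo difference in change is (-d) - (-d) = 0 within each subject at each visit. Only a difference between the two eyes remains.

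**4. Variability across Phases 1, 3 and 4.** For a baseline or a fully cleared change score, the added variance per visit is p(1 - p)d². With p = 0.3 and d = 2 s this is 0.3 × 0.7 × 4 = 0.84 s². Take an assumed between-visit difference SD of 2.0 s, and let ρ be the correlation of recent use between visits. The SD becomes √(4 + 2 × 0.84 × (1 - ρ)):
- ρ = 0: √5.68 = 2.38 s
- ρ = 0.5: √4.84 = 2.20 s
- ρ = 1: √4 = 2.00 s

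A second illustration takes within-subject variance as half of a total of 1, with carry-over at a random half of a user's visits. The within-subject SD rises by the factor √[(0.5 + 0.25 f r²)/0.5]. This is 0.2% at f = 0.1, r = 0.25 and 12% at f = 0.5, r = 1.

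**5. Post-wear TBUT.** Objective (iii) concerns TBUT after VCO lens wear. There the added variance per visit is p(1 - p)(kd)². For p = 0.3 and d = 2 s:
- k = 0: bias -0.6 s, added variance 0
- k = 0.5: bias -0.3 s, added variance 0.3 × 0.7 × 1 = 0.21 s²
- k = 1: bias 0, added variance 0.84 s²

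The two harms trade off. An effect that clears fully biases the change and leaves post-wear variability alone. One that persists does the opposite.

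**The case against.** **The fellow eye is a control.** Both eyes are measured at baseline and the other eye wears a placebo lens. If drops or habitual lenses are used in both eyes, which is an assumption but a natural one, the residual largely cancels within the subject. This stands. It defeats any inference that the VCO-versus-placebo comparison is itself invalid. It does not protect the comparison over time, which is the only one the plan states.

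**Objective (iii) is about readings after wear.** A reader might infer that its variability is contaminated throughout. Step 5 shows this needs an effect that outlasts the lens. The point therefore covers baseline or change-score variability, and post-wear variability only conditionally. Habitual use is also likely to be correlated between visits, so the 2.38 s figure, which assumes independence, is at the high end for its inputs.

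**Frequency is not shown.** A reader might infer that the typical enrolled subject uses a lubricant. The documents describe dry-eye sufferers and usual practice in general. Entry needs a symptom score, not a diagnosis or prior treatment. What follows is that users are allowed in and some are likely.

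**The contact-lens half is thinner.** Nothing says that entrants wear lenses or that recent wear shifts TBUT in a given direction. This half rests only on the absence of an exclusion or a lens-free rule.

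**The remedy may be awkward.** Someone who instils drops often may be hard to book after a fixed interval. This stands as a cost.

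**Conclusion.** The concern holds in limited form. The eligibility, screening and phase sections allow a baseline taken soon after a lubricant drop or lens wear, and nothing in the plan would reveal it afterwards. The exposed quantities are the comparison over the three time points for TBUT and Schirmer, and any baseline or change-score TBUT variability across Phases 1, 3 and 4.

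Size and direction are unknown. Under the assumed inputs the effect on the mean change runs from minor (80% power falling to 74%) to serious (9%), while the effect on pooled variability is smaller. These figures rest on assumed shares, shifts and clearance. They show that the effect could matter, not that it does. The change is still worth making, because it is cheap beforehand and cannot be recovered once timing has gone unrecorded.

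**What to change.** - At each of the four visits, record the time of the last eye drop and of the last contact-lens wear, for each eye.
- Take the pre-lens reading only after one fixed drop-free and lens-free interval, chosen by the investigators and identical at all visits. Book sessions around the subject's usual use, and rebook within the phase's 5-week window when the interval is not met.
- In Statistical Analysis, name the VCO-minus-placebo difference in change as the comparison for objectives (i) and (ii). This removes most of the bias from an effect shared by both eyes, but not the noise in single-eye variability, so it complements the interval rule.
- State whether objective (iii) uses the post-wear reading, the baseline or the change.

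The cost is a sentence in each phase, a short addition to the case-report form, a sentence or two in the analysis section and occasional rebooking. No extra subjects or procedures are needed. The downside is that some frequent drop users may be harder to schedule. Because the efficacy analysis is limited to completers, the number lost for this reason should be reported.
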